### 2. Background

Achieving optimal prosthetic alignment of the femoral, tibial and patellar components during Total Knee Replacement (TKR) is of great importance as it contributes to better function, less pain and improved quality of life. TKR requires accuracy in the execution of bone cuts in the correct orientation to the coronal, sagittal and axial planes. Malposition potentially leads to increased mechanical stress on the bearing surfaces and inevitably to earlier loosening.

Computed Axial Tomography (CT) is the gold standard technique to evaluate implant alignment in the coronal, sagittal and axial planes. As such, CT has imaging been used to create custom instrumentation with purported likely improvement in surgical outcomes. Customized instrumentation created from a preoperative CT has been shown to be safe and effective, with no reported difference in patient outcomes and similar total knee arthroplasty component alignment. However, taking into consideration CT's high levels of radiation, cost expenses and its inability to obtain images of the limb in weight-bearing position, CT scan cannot be used routinely as a postoperative tool to evaluate TKR implant positioning.

The imaging system manufactured by EOS Imaging (formerly Biospace Med, Paris) is a biplanar, low-dose radiation, full body, high resolution, radiological imaging system allowing simultaneous acquisition in the coronal and sagittal planes and in standing position. EOS' main benefits are the considerable reduction in radiation dose (up to 1000 times less than for CT and ten times less than the plain radiography) by using a gaseous detector. George Charpak, the inventor, was awarded the Nobel Prize in 1992 for this work. Moreover, the EOS system can provide 3D images by using the appropriate software algorithms, thus providing a low-radiation alternative to CT.

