**PROTOCOL TITLE: Manual vs. custom knee study**

transmitted securely using Box.com in a dicom format.

Secondary outcomes of operative time and intraoperative blood loss will be obtained from the medical record. Wilcoxon Rank-Sum test will be used to compare the coronal, sagittal, and axial alignment measurements between groups. Student's t-test will be used to compare the secondary outcome measures of operative time and intraoperative blood loss between groups.

A power analysis was performed to determine appropriate sample size for each group to determine a 1 degree difference in component alignment. Previous literature has noted standard deviation in axial alignment with custom instrumentation is 1.5 degrees. With a p-value of 0.05 and a power of 0.8, our power analysis determined that each group needed to include 25 subjects to be appropriately powered. The planned sample size of 28 subjects in each group was chosen to fulfill this power analysis.

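### The power calculation takes its only SD from custom-instrumented knees and gives none for manual knees; even with that SD in both arms, 28 per group gives about 69% two-sided power, not 80%

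*Combined protocol and SAP*

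**What the plan says.** Section 11 (Data and Specimen Management) makes component alignment, compared with the preoperative CT plan, the primary outcome. The power analysis was done "to determine a 1 degree difference in component alignment". Its one input for spread is "Previous literature has noted standard deviation in axial alignment with custom instrumentation is 1.5 degrees". The error rates are given as "With a p-value of 0.05 and a power of 0.8", with no statement of sidedness. The result is that "our power analysis determined that each group needed to include 25 subjects to be appropriately powered", and then "The planned sample size of 28 subjects in each group was chosen to fulfill this power analysis".

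The planned analysis is also in Section 11: "Wilcoxon Rank-Sum test will be used to compare the coronal, sagittal, and axial alignment measurements between groups". Section 9 defines four groups covering every combination of custom and manual preparation of femur and tibia. Objective 3 (Section 1) and endpoint 3 (Section 8) concern the difference between manual and custom instrumentation. No SD for manual instrumentation appears anywhere, and nothing is said about unequal variances.

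**The concern.** A two-group power claim needs the spread in both groups. Here one side of the comparison has a cited value and the other has none. That 1.5 was carried over to manual knees is an inference, but no other value is available in the documents. The cited value is also for the axial plane only, while the same test is planned for the coronal and sagittal planes.

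The stated 0.8 power will shape how a non-significant result is read. If the true power for custom against manual is well below 0.8, a null finding could be taken as good evidence that the two methods align components alike, when the trial had a substantial chance of missing a 1 degree difference.

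**Working it through.** **Inputs from Section 11.** Difference 1 degree; SD 1.5 (custom, axial); alpha 0.05; power 0.80; 25 per group required, 28 planned (4 × 28 = 112, matching Sections 4 and 23). **Assumed.** A two-sided test, because sidedness is not stated; a manual SD of 1.5, 2.0 or 2.5, because none is given; and alignment analysed as signed deviation with a shift in mean.

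**Step 1: the plan's own figure.** With a common SD,

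n per group = 2 (z₀.₉₇₅ + z₀.₈₀)² SD² / difference² = 2 × (1.960 + 0.842)² × 2.25 / 1 = 35.3, so 36.

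The noncentral t gives 37. The stated 25 is not reproduced. A one-sided test gives 2 × (1.645 + 0.842)² × 2.25 = 27.8, so 28 (noncentral t: 29). That equals the planned size, but not the stated requirement of 25. To get 25 two-sided, the common SD would have to be √(25/2) / 2.802 = 1.26. A one-way analysis of variance on four groups, two with mean 0 and two with mean 1 degree, needs 26, which is close, but the plan describes no such analysis.

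**Step 2: power with SD 1.5 in both arms.** Noncentral t, two-sided 5%: 64% at 25 per group and 69% at 28. The normal approximation gives 65% and 70%. A 10,000-run simulation of the planned Wilcoxon test on normal data gives 61% and 66%. So the fall from 80% to 69% arises before any question about the manual SD.

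**Step 3: power with a larger manual SD, s.** The standard error is SE = √((1.5² + s²)/n), the noncentrality is 1/SE, the degrees of freedom are Satterthwaite's, and power is the noncentral t probability beyond the upper 2.5% point.

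| Contrast | Manual SD s | SE | 1/SE | Power (noncentral t) | Power (simulated Wilcoxon) |
|---|---|---|---|---|---|
| 28 v 28 | 1.5 | 0.401 | 2.49 | 69% | 66% |
| 28 v 28 | 2.0 | 0.472 | 2.12 | 55% | 52% |
| 28 v 28 | 2.5 | 0.551 | 1.81 | 43% | 41% |
| 56 v 56 | 1.5 | 0.283 | 3.53 | 94% | 93% |
| 56 v 56 | 2.0 | 0.334 | 2.99 | 84% | 82% |
| 56 v 56 | 2.5 | 0.390 | 2.57 | 72% | 71% |

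The 56 v 56 rows pool by bone: A and B against C and D for the femur, A and D against B and C for the tibia. By noncentral t, pooled power is 80.7% at a manual SD of 2.15 and 79.5% at 2.2, so it drops below 80% near 2.2.

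**Step 4: separating the two effects at 28 v 28.** From 80% to 69% is the arithmetic error (11 points). From 69% to 55% (14 points) or to 43% (26 points) is the effect of the manual SD, and only if that SD is 2.0 or 2.5.

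**The case against.** The strongest reply is that a common SD is an ordinary planning assumption and nothing in the documents contradicts it. A reader might infer that custom guides place components more consistently, so that the manual SD must exceed 1.5 and power is overstated for that reason. The documents do not support this. The Background remark that "CT has imaging been used to create custom instrumentation with purported likely improvement in surgical outcomes" concerns outcomes, calls the benefit purported, and does not mention variability. The next sentence there reports similar component alignment with custom instrumentation. It does not establish equal variances either, so the manual SD remains simply unstated.

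Second, the four groups form a 2 × 2 layout by bone, and pooling gives 56 against 56, where power stays at 80% or more until a manual SD of about 2.2. This is right, and it may be the contrast closest to Objective 3. But Section 11 sizes each group and describes comparison between groups; it does not state pooling.

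Third, the direction of the effect depends on how deviation is analysed. Alignment is compared with the preoperative plan, and the documents do not say whether deviations are signed or absolute. On absolute deviations, larger manual spread is itself the signal: with no mean bias, simulated Wilcoxon power at 28 v 28 is about 21%, 52% and 76% at manual SDs of 2.0, 2.5 and 3.0, rising rather than falling. This stands, and limits Step 3 to signed deviations.

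Fourth, a one-sided test with SD 1.5 in both arms would have about 79 to 80% power at 28 per group. The plan does not say that the test is one-sided.

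A reader might also want to add EOS reading error to the 1.5 degrees, since EOS accuracy is under study. The published SD may already include measurement error, and the documents give no size for it, so no figure is offered.

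**Conclusion.** The point holds in limited form. The calculation rests on a single SD, for custom instrumentation in the axial plane, and leaves the manual SD unstated. For a two-sided comparison of one group with another, the stated 0.8 power is not reached at any manual SD of 1.5 or more: it is about 69% at best with 28 per group, and 64% if only 25 can be analysed. That base shortfall is an arithmetic error and should not be attributed to the source of the SD.

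The further loss, to 55% or 43%, is conditional on an assumed manual SD of 2.0 or 2.5 and on signed deviations with a 1 degree mean shift. It shows how sensitive the claim is; it is not evidence that manual spread is in fact larger. If the contrast of interest is custom against manual pooled by bone, power is adequate up to a manual SD of about 2.2, but the plan would have to say that this is the contrast.

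**What to change.** In Section 11:

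- State which contrast is powered (group against group, or custom against manual pooled by bone) and whether the test is one- or two-sided.
- State whether the analysed quantity is signed or absolute deviation from the plan.
- Give a sourced SD for manual knees, or declare equal SDs as an assumption and show a sensitivity range; 1.5 to 2.5 degrees would do as an illustration, labelled as assumed.
- Replace the 0.8 power and the statement that 25 per group is sufficient with the recomputed power for the named contrast at the planned size.

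This changes protocol wording only. No patients are added and no procedure changes. The cost is a less favourable power statement if the contrast is group against group.

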**11. Data and Specimen Management**

The primary outcome measure of total knee arthroplasty component alignment will be measured on the postoperative EOS image obtained at the six week follow-up appointment. Alignment will be measured in the coronal, sagittal and axial planes and compared to the preoperative plan created with the preoperative CT. All TKR implant alignment measures for both the pre and post op radiographs will be done by the manufacturer of the EOS Imaging system. All radiographs sent to EOS Imaging will be fully de-identified and will be

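### The stated 25 per group for 1 degree at SD 1.5 and 80% power cannot be reproduced: a two-sided test needs 37 (t) and a one-sided test 29; the planned 28 gives 66–69% two-sided

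*Combined protocol and SAP*

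**What the plan says.** The whole sample-size justification is one paragraph in Section 11 (Data and Specimen Management). The aim is "to determine a 1 degree difference in component alignment". The variability comes from earlier literature: "standard deviation in axial alignment with custom instrumentation is 1.5 degrees". The error rates are given as "With a p-value of 0.05 and a power of 0.8". The result is that "our power analysis determined that each group needed to include 25 subjects to be appropriately powered", followed by "The planned sample size of 28 subjects in each group was chosen to fulfill this power analysis".

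The same section names the analysis: "Wilcoxon Rank-Sum test will be used to compare the coronal, sagittal, and axial alignment measurements between groups". It defines the primary outcome over three planes: "Alignment will be measured in the coronal, sagittal and axial planes and compared to the preoperative plan created with the preoperative CT".

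Section 9 (Procedures Involved) defines four randomised arms. Sections 4 and 23 give a total of 112, which is 4 × 28, so the group being sized is an arm.

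The protocol does not state the sidedness, the test used for sizing, which groups are contrasted, or any allowance for dropout. The step from 25 to 28 is not explained.

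**The concern.** Every number needed to check the calculation is printed, and 25 looks too small for a standardised difference of 1/1.5 = 0.667 at 80% power. If it is wrong, the claim that 28 per arm meets the 80% target is in doubt too.

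This is the only power statement in the protocol, and it concerns the primary outcome. Readers will rely on it to interpret a null result. If real two-sided power is nearer two-thirds, a non-significant difference between two arms could be over-read as evidence that custom and manual instrumentation agree to within 1 degree.

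A second weakness is the SD. It is described as applying to axial alignment with custom instrumentation, but is used without comment for manual instrumentation and for the coronal and sagittal planes.

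**Working it through.** **Inputs (Section 11).** Difference Δ = 1 degree; SD σ = 1.5 degrees, taken as common to both groups because no other is given; α = 0.05; power 0.80; equal groups. Sidedness is not stated, so both are tried.

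**Attempt to reproduce 25.** Normal approximation for two means, n per group = 2(z_α + z_β)²σ²/Δ²:

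- Two-sided: 2 × (1.96 + 0.8416)² × 2.25 / 1 = 35.3, so 36.
- One-sided: 2 × (1.645 + 0.8416)² × 2.25 / 1 = 27.8, so 28.

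The noncentral t gives 36.3 (37) two-sided and 28.5 (29) one-sided. For the Wilcoxon test, simulation on normal data (100,000 runs, with and without continuity correction where a range is shown) gives two-sided power of 79.4–79.7% at 38 and 80.6–80.9% at 39. One-sided, it gives 78.8% at 29 and 79.9% at 30.

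| | Normal | t | Wilcoxon (normal data) |
|---|---|---|---|
| n per group, two-sided | 36 | 37 | about 39 |
| n per group, one-sided | 28 | 29 | about 30 |
| Power at 25, two-sided | 65.4% | 63.7% | about 61% |
| Power at 25, one-sided | 76.2% | 75.1% | 73% |
| Power at 28, two-sided | 70.3% | 68.8% | about 66% |
| Power at 28, one-sided | 80.2% | 79.3% | 77–78% |

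No cell gives 25 as the requirement, and 25 per group reaches 80% in none of them.

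**What would make the figures true.** By two-sided t-test, 80% power for 1 degree needs a common SD of at most 1.24 at 25 per group, or 1.31 at 28. Neither rounds to 1.5. Holding the SD at 1.5, the difference detectable with 80% power at 28 per group is 1.14 degrees (t) or about 1.18 degrees (Wilcoxon).

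**Other designs tried.**

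- One-sample or paired formulas give 14 to 20.
- Unequal 3:1 allocation gives 24 in the smaller group (two-sided), but the planned groups are equal.
- A four-group one-way ANOVA with arm means 0, 0, 1, 1 gives 79.0% at 25, 80.8% at 26 and 84.0% at 28. With means 0, 0.5, 0.5, 1 it gives 46.7% at 25 and 51.8% at 28.

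**Scale of the gap.** Four arms of 37 to 39 would total 4 × 37 = 148 to 4 × 39 = 156, against 4 × 28 = 112.

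**Sensitivity to the SD.** No manual SD is given. Keeping 1.5 for custom and assuming 1.0 to 2.5 for manual, the effective SD is √((1.5² + s²)/2), which is 1.27 at s = 1.0 and 2.06 at s = 2.5. Two-sided t power at 28 v 28 then runs from 82% down to 43%.

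**The case against.** The strongest reply is that the test may have been meant as one-sided. The planned 28 is exactly the one-sided normal-approximation sample size (27.8 rounded up, power 80.2%). On that reading the trial is about the right size and only the intermediate 25 is wrong. This stands in part: the shortfall at 28 is material only if the test is two-sided. But the protocol states no direction, and its third objective is to evaluate differences, which would ordinarily be read as two-sided. Under a t or Wilcoxon sizing, 28 also falls just short of the 29 or about 30 needed one-sided.

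The second reply is that 25 may come from a four-group ANOVA. For a femoral component, arms A and B are custom and C and D manual; for a tibial component, A and D are custom and B and C manual. Means of 0, 0, 1, 1 are therefore a natural pattern, and they need 26. This is the nearest route to 25, but it still misses by one. The protocol names no ANOVA; it names the rank-sum test for alignment.

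The third reply is that manual versus custom can be compared for each bone by pooling two arms, 56 v 56, with about 93–94% two-sided power at SD 1.5. That is true and limits the practical harm, but no pooled or factorial analysis is specified and the power paragraph sizes each arm.

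Finally, Section 9 speaks of 20 patients enrolled and 60 remaining (20 + 60 = 80), not 112. Every figure here for 28 per arm assumes that the total of 112 is correct.

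**Conclusion.** The concern holds. The 25 per group does not follow from the protocol's own inputs in a two-sample comparison of equal groups, one-sided or two-sided, by any of the three methods tried. That conclusion is firm.

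The consequence for the planned size is conditional. For a two-sided comparison of one arm with another, 28 per arm gives 69% (t) or 66% (Wilcoxon) power, and the 80% claim is wrong; the plain normal approximation, at 70%, does not change this. For a one-sided comparison, 28 gives 77–80%, and mainly the printed 25 needs correcting.

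These figures rest on a common SD of 1.5 degrees, complete data on 28 per arm and no multiplicity adjustment for the three planes or the several arm comparisons. The Wilcoxon figures also assume normal data and need not hold if absolute deviations from the preoperative plan are analysed.

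**What to change.** Correct the power paragraph in Section 11:

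1. State the sidedness and the test used for sizing.
2. Replace 25. If two-sided, use 37 (t) or about 39 (Wilcoxon, normal data). If one-sided, use 29 (t) or about 30 (Wilcoxon, normal data).
3. Delete the sentence saying that 28 per group was chosen to satisfy the power analysis. If two-sided, put in its place: *The planned 28 per arm gives about 66–69% power for a 1 degree difference between two arms at SD 1.5, and 80% power only for about 1.14 degrees (t) or 1.18 degrees (Wilcoxon, normal data).* If one-sided, state that 28 gives 79% (t) or 77–78% (Wilcoxon, normal data).
4. State that the SD of 1.5 is for axial alignment with custom instrumentation only, and is assumed for manual instrumentation and for the other planes.

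This costs wording only and adds no patients. The price is a less favourable stated power, 66–69% instead of 80% if two-sided.

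Optional and separate, by amendment before the data are analysed: prespecify pooled contrasts, A+B v C+D for the femur and A+D v B+C for the tibia. At 56 v 56, two-sided power is about 93–94% at SD 1.5, 82–84% if the manual SD is assumed to be 2.0, and 69–72% if it is assumed to be 2.5. This requires no important femur-by-tibia interaction and confirmation of the total of 112. It changes the analysis specification, and the correction above does not depend on it.

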**12. Provisions to Monitor the Data to Ensure the Safety of Subjects**

N/A

**13. Withdrawal of Subjects\***

N/A

**14. Risks to Subjects\***

Procedures such as X-rays and CT scans will be used during this research study. The cumulative radiation exposure from these tests is considered small and is not likely to adversely affect the patient or their disease. However, the effects of radiation add up over a lifetime. It is possible that having several of these tests may add to the patient's risk of injury or disease. When deciding to enter this study, the patient will be asked about their past and future contact with radiation.

There are no other known risks involved in this study since both type of knee implants are FDA approved standard implants used by [name] and [name] in surgery.

The EOS imaging system is being used to obtain full standing radiographs. This is within its FDA approved capacity.

The ad hoc analyses of the EOS radiographs for TKR alignment is independent of the patient's care at NMG and performed after the surgery and post-operative care has been completed. The radiographs obtained in EOS are obtained for the patient's standard of care with their surgeon.

**15. Potential Benefits to Subjects**

**PROTOCOL TITLE: Manual vs. custom knee study**

The subjects are not likely to have any direct benefit from being in this research study. However, the subject may benefit from the knowledge that they are helping to improve our understanding of how best to treat future patients that undergo total knee arthroplasty.

**16. Vulnerable Populations**

N/A

**17. Community-Based Participatory Research**

N/A

**18. Sharing of Results with Subjects**

No results will be shared with the subjects.

**19. Setting**

All research will be conducted in the orthopaedic surgery clinic [[name]].

- All subjects will be identified during their pre-operative visit with [name] or [name].
- All consent will be obtained at the orthopaedic surgery clinic [[name]].

**20. Resources Available**

[name] and [name] has been conducting clinical research for the last 8 years of their careers Furthermore, [name] and [name] will have support from joints fellow [name] and the research coordinator in the department that will facilitate the identification, consent and collection of data expeditiously. Northwestern Memorial Hospital cares for approximately 700 orthopaedic joint surgery patients per year, from which the study population will be derived. Lastly, coordinator and statistical arrangements are already in place and are ready to implement.

**21. Prior Approvals**

N/A

**22. Recruitment Methods**

Subjects will be enrolled in the study in the outpatient clinic [[name]] at their pre-operative clinical appointment with either [name] or [name]. The principal investigator or sub-investigator will complete the informed consent process and complete the written consent form.

**23. Local Number of Subjects**

112

**PROTOCOL TITLE: Manual vs. custom knee study**

**24. Confidentiality**

N/A

**25. Provisions to Protect the Privacy Interests of Subjects**

Only the Principal Investigator, Co-Investigators, and authorized study staff will access to the data collected through the study. All research team members will be required to complete the CITI research training along with other requisite training required to access medical records.

**26. Compensation for Research-Related Injury**

N/A

**27. Economic Burden to Subjects**

All procedures performed in the study are part of the subject's standard of care while undergoing treatment with [name] and [name]. All costs incurred from the study procedures, visits, etc. will therefore be billed to the patient's insurance. The patient will therefore incur no cost from the study.

**28. Consent Process**

All subjects will be consented during the patient's pre-operative clinic visit with [name] or [name] by either [name], [name], [name], or the authorized research coordinator. The patient will be given the choice to take a copy of the consent home to review prior to making a decision regarding their participation in the study. All the patient's questions will be answered prior to obtaining informed consent.

